#### 14.4.2 Key Secondary Efficacy Endpoints and Analyses

Following the similar formula mentioned in the previous section, the following  $SPID_{MOVE}$  for the different time intervals will be estimated and compared for the 2 treatment groups using the same ANCOVA model.

- $SPID_{MOVE}$  over the following intervals: 0-6, 6-12, 0-12, 12-24, 24-36, 0-36, 24-28, 36-48, and 0-48 hours post- $T_0$ . The mean  $SPID_{MOVE}$  for 0-6, 6-12, 0-12, 12-24, 24-36, 0-36, 24-28, 36-48, and 0-48 hours post- $T_0$  will be compared between the 2 treatment groups (active versus vehicle) using an ANOCVA model with the baseline pain/soreness score as the covariate.

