	
15 morphine equivalents units per day for greater than 3 out of 7 days per week in any 1-month period within 12 months prior to Day 1.
 
12. Have received an opioid within 30 days prior to Day 1.
 
13. Routine use (defined as 3 out of 7 days per week) of any analgesic drug (over-the-counter [OTC] or prescription).
 
14. Consumption of any medication (prescription or OTC medications, vitamins, minerals, and dietary supplements) within 2 weeks prior to Day 1. Exception: continuing hormonal contraception and hormone replacement therapy is allowed.
 
15. Any history of drug or alcohol abuse (according to the investigator’s judgment) in the prior 5 years.
 
16. The subject has received an investigational drug or device within 3 months prior to screening.
 
17. The subject has participated previously in this trial or the subject has participated in another clinical trial involving exercise of the upper extremities within the last 6 months.
 
18. The subject is an employee or relative of an employee of the study site directly involved with the study.
 
19. Any medical or other condition that, in the opinion of the investigator, might affect the subject’s ability to safely complete all study procedures (including the exercise regimen) or might interfere with the efficacy results of the study.

EFFICACY VARIABLES
	
Primary Endpoint: Sum of the time-weighted pain intensity differences from baseline with movement (SPIDMOVE) over 0-24 hours post-T0 (SPIDMOVE 0-24 hr).
 
Key Secondary Endpoints:
 
 
1. SPIDMOVE over the following intervals: 0-6, 6-12, 0-12, 12-24, 24-36, 0-36, 24-48, 36-48, and 0-48 hours post-T0.
 
 
Other Secondary Endpoints:
 
 
1. Sum of time-weighted differences from baseline in muscle stiffness with movement (SSIDMOVE) over the following intervals: 0-6, 6-12, 0-12, 12-24, 0-24, 0-36, 24-48, and 0-48 hours post-T0.
 
2. Total relief with movement (TOTPARMOVE) 0-6 hours post-T0.
 
3. Subject’s global assessment of study medication assessed at approximately 48 hours post-T0 (or upon early termination, if applicable).
 

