### 10.2.3 Other Secondary Endpoints:

- Sum of time-weighted differences from baseline in muscle stiffness with movement (SSIDMOVE) over the following intervals: 0-6, 6-12, 0-12, 12-24, 0-24, 0-36, 24-48, and 0-48 hours post-T0.
- Total relief with movement (TOTPARMOVE) over 0-6 hours post-T0.
- Subject's global assessment of study medication assessed at approximately 48 hours post-T0 (or upon early termination, if applicable).

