## 14 STATISTICS

Detailed methodology for summary and statistical analyses of the data collected in this study will be documented in a Statistical Analysis Plan, which will be signed off prior to the database lock.

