## 14.4 Efficacy Analysis

All statistical testing will be performed with a 2-sided 0.05 level of significance. For each of the time intervals analyzed, completion of administration of the first dose of study drug is considered time 0, T0. Efficacy parameters will be analyzed using both the FAS and the PPS.

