### 14.4.1 Primary Efficacy Endpoint and Analysis

The primary efficacy outcome is the sum of the time-weighted differences from baseline in muscle pain/soreness with movement (SPIDMOVE) over 0-24 hours post-T0 (SPIDMOVE 0-24h), that is the area under the differences from baseline pain/soreness intensity difference curve.

The PIDs with movement from time point A to time point B will be calculated using the trapezoid rule by subtracting each post-T0 pain score with movement from the pain score with movement at time point Ti as follows:

- PID with movement at time point i (PIDMOVE i) = NRS score with movement at time point i – NRS score with movement at baseline.
- Mean of adjacent pain intensity differences MMOVE i = (PIDMOVE i + PIDMOVE i+1) / 2
- The weight given to each MMOVE i score (Wi) = elapsed time to the next evaluation (ti+1 – ti).
- SPIDMOVE A-B hr =  $\sum_{i=A}^{B-1} W_i M_{MOVE i}$  where i refers to each NRS scheduled assessment time point between A and B (not including B).

Thus, SPIDMOVE 0-24h =  $\sum_{i=0}^{18} W_i M_{MOVE i}$ , where i refers to each NRS scheduled assessment time point between baseline and 24 hours.

The general formula for computing SPID between any two time points a and b is as follows:

$$SPID_{a-b} = \sum_{i=a}^{b-1} \frac{(t_{i+1} - t_i)(PID_{i+1} + PID_i)}{2}$$

Where i refers to each scheduled assessment time point between a and b hours post baseline,  $t_i$  is the  $i$ th time point and  $PID_i$  is the pain intensity difference at time  $i$

The mean  $SPID_{MOVE}$  for 0-24 hours post- $T_0$  will be compared between the 2 treatment groups using an analysis of covariance (ANCOVA) model with baseline pain/soreness score as a covariate.

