#### 14.4.3 Other Secondary Analyses

The following other secondary endpoints for different time intervals will be compared between the 2 treatment groups using an ANCOVA model with the baseline pain/soreness score as the covariate.

- $SSID_{MOVE}$  over the following intervals: 0-6, 6-12, 0-12, 12-24, 0-24, 0-36, 24-48, and 0-48 hours post- $T_0$ . The mean  $SSID_{MOVE}$  for 0-6, 6-12, 0-12, 12-24, 0-24, 0-36, 24-28, and 0-48 hours post- $T_0$  will be compared between the 2 treatment groups (active versus vehicle) using an ANOCVA model with the baseline muscle stiffness score as the covariate.
- $TOTPAR_{MOVE}$  over 0-6 hours post- $T_0$ . An ANOVA model will be used for these efficacy endpoints.

$TOTPAR_{MOVE}$  A-B hr =  $\sum_{i=A}^{B-1} PR_i H$  where  $i$  refers to each pain relief scheduled assessment time point between A and B (not including B).

The TOPAR endpoints will be compared between the 2 treatment groups using an ANOVA model.

The subject's global assessment of efficacy will be assessed at approximately 48 hours post-T0 (or upon early termination if the subject withdraws prior to the 48-hour assessment). The distribution of 5 categories (poor, fair, good, very good, or excellent) will be compared between the 2 treatments (active versus vehicle) using the Chi-Squared test. In addition, the 5 categories will be dichotomized into 2 categories (good/very good/excellent versus poor/fair). The proportion of good, very good, and excellent ratings will be calculated for each treatment. This proportion will be compared between the 2 treatments (active versus vehicle) using the Fisher's Exact test.

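### Section 14.4.2 prints SPID 24–28 h where 24–48 h is the declared key secondary, and nine key windows are each tested at 0.05 with no visible multiplicity rule

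*Combined protocol and SAP*

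**What the plan says.** **Windows.** The Synopsis declares the key secondary SPID endpoints "over the following intervals: 0-6, 6-12, 0-12, 12-24, 24-36, 0-36, 24-48, 36-48, and 0-48 hours", and Section 10.2.2 gives the same nine. Section 14.4.2, which sets out their analysis, has them "over the following intervals: 0-6, 6-12, 0-12, 12-24, 24-36, 0-36, 24-28, 36-48, and 0-48 hours"; its second sentence repeats that list. For stiffness (SSID), Section 10.2.3 declares windows "over the following intervals: 0-6, 6-12, 0-12, 12-24, 0-24, 0-36, 24-48, and 0-48 hours". The first list in the SSID bullet of Section 14.4.3 agrees, but the analysis sentence that follows reads "0-6, 6-12, 0-12, 12-24, 0-24, 0-36, 24-28, and 0-48 hours".

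**Method.** Section 14.4.1 defines SPID by the trapezoid rule and extends it to any interval: "The general formula for computing SPID between any two time points a and b is as follows". Section 14.4.2 applies the primary ANCOVA model to every window.

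**Error control.** Section 14.4 states: "All statistical testing will be performed with a 2-sided 0.05 level of significance". Sections 14.4 to 14.4.3 contain no gate on the primary, no testing order, no adjustment and no statement that the secondary windows are descriptive. These sections carry no redaction marks. Section 14 defers detail: "Detailed methodology for summary and statistical analyses of the data collected in this study will be documented in a Statistical Analysis Plan". That SAP is not part of the text available here.

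**The concern.** There are two separate defects in the same section.

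(a) The analysis text does not match the endpoint list. Read literally, the declared 24–48 h comparison has no stated analysis, and a 4-hour window that nobody declared is tested. The slip occurs three times, so it could be carried into the SAP or the programs.

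(b) The protocol separates key from other secondary endpoints but gives the key tier no rule for inference. Nine overlapping windows, each tested at 0.05, give an ineffective drug more than a 5% chance of at least one significant window. The protocol also does not say how to read a significant window when SPID 0–24 h is not significant. This matters only if a confirmatory claim is made on a key window and the SAP adds no rule.

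**Working it through.** **(a) The lists side by side.** The entry in question is the seventh in every list.

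| Place | SPID | SSID |
|---|---|---|
| Synopsis | 24–48 | 24–48 |
| 10.2.2 / 10.2.3 | 24–48 | 24–48 |
| 14.4.2 / 14.4.3, first list | **24–28** | 24–48 |
| 14.4.2 / 14.4.3, second list | **24–28** | **24–28** |

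Three entries differ, and the other eight SPID windows match throughout. The misprinted window covers 4 of the declared 24 hours. No data are lost: under the trapezoid rule SPID 24–48 = SPID 24–36 + SPID 36–48, and both parts are listed.

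**(b) Error rate over the nine windows, using the corrected list.** Five windows are disjoint (0–6, 6–12, 12–24, 24–36, 36–48). The other four (0–12, 0–36, 24–48, 0–48) are unions of these. The independence figure, 1 − 0.95⁹ = 0.370, is therefore too high, and the overlap has to be modelled.

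Inputs from the protocol: nine windows, two-sided 0.05 (|z| > 1.96), trapezoid weights. Assumptions: assessment times (redacted) and correlations between scores (not given). With weight vectors w and score correlation matrix C, the correlation between the test statistics of windows a and b is

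w_a′Cw_b / √(w_a′Cw_a · w_b′Cw_b).

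Three grids were simulated, with 400,000 draws each:

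- G1: hourly from 0 to 48 h.
- G2: hourly to 14 h, then 2-hourly to 48 h. This gives 14 + 5 = 19 intervals in 0–24 h, matching the sum from i = 0 to 18 in Section 14.4.1, "where i refers to each NRS scheduled assessment time point between baseline and 24 hours".
- G3: as G2 to 24 h, then 6-hourly to 48 h.

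Chance of at least one significant window when the drug has no effect at any time:

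| Grid | Equal correlation 0.3 / 0.5 / 0.7 | Decaying, 0.5 / 0.7 / 0.85 per 12 h | Equal correlation 0.9 |
|---|---|---|---|
| G1 | 0.128 / 0.101 / 0.083 | 0.181 / 0.148 / 0.116 | 0.067 |
| G2 | 0.141 / 0.109 / 0.089 | 0.181 / 0.148 / 0.117 | 0.069 |
| G3 | 0.158 / 0.125 / 0.098 | 0.180 / 0.147 / 0.116 | 0.073 |

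The last column comes from a separate run of 200,000 draws. The extreme case of uncorrelated disjoint windows gives 0.276.

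Chance of a significant window without a significant primary, again with no drug effect: 0.032–0.132 on G1, 0.039–0.132 on G2 and 0.048–0.131 on G3. At equal correlation 0.9 it is 0.016–0.024.

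**What a gate on the primary achieves.** With no drug effect the overall error cannot exceed 0.05 (simulated 0.049–0.051, which is simulation noise). If the drug acts only up to 24 h, the windows 24–36, 24–48 and 36–48 are still null. The chance that at least one of them is significant after the gate is:

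| Power of the primary | Three grids, excluding equal correlation 0.9 | Five-piece model, correlation 0.95 to 0 |
|---|---|---|
| 80% | 0.031–0.064 | 0.032–0.091 |
| 90% | 0.031–0.073 | 0.032–0.103 |
| Certain to pass | 0.062–0.091 | 0.064–0.115 |

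Gate plus Holm over the nine windows gives 0.011–0.018 in this scenario at 80% or 90% primary power.

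**Power cost of Holm.** The first step is 0.05/9 = 0.0056, with critical value 2.773. A window with 80% power at 0.05 has mean z = 1.960 + 0.842 = 2.802, so its power at that step is Φ(2.802 − 2.773) = 0.51. For 90% power, Φ(3.242 − 2.773) = 0.68.

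**The case against.** Part (a) is a misprint with little practical consequence. The correct window is declared twice, the formula and model cover any interval, and a competent programmer would probably notice. The assessment times are redacted, so it is not even certain that a 28-hour assessment exists; on grid G3 there is none. All of this stands. It makes the correction simple, but Section 14.4.2 is the operative analysis text and contradicts the endpoint section.

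Part (b) rests on a document not seen. Gates and testing orders are often placed in the SAP, and silence in the protocol does not show that the trial has no rule. There is one primary endpoint with one test, and no visible text says that a claim will rest on a secondary window; nominal secondary p-values could be read as supportive. This also stands, and it limits the point to confirmatory use of the key windows.

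The size depends on assumed correlations. An equal correlation of 0.9 brings the error to about 0.07, below the 0.083 found with the other settings, and the 0.276 case needs uncorrelated pain scores within a subject, which is implausible. That is a fair limit on precision. It does not remove the excess, which is above 0.05 in every setting tried.

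**Conclusion.** Both parts hold. (a) Three entries are wrong as printed, almost certainly through a typing error; neither the method nor the data are in doubt. (b) The visible protocol gives no rule for nine key windows tested at 0.05 each. The overall error with no drug effect is 0.083–0.181 on the assumed grids, falling to about 0.07 at a uniform correlation of 0.9. These figures illustrate the size and are not estimates for this trial, because they rest on assumed assessment times and correlations. The primary test is not inflated. The section should be amended, but the main conclusion of the trial is not at risk. Confidence is medium, because the SAP may already settle (b).

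**What to change.** (a) Replace 24–28 with 24–48 in both lists of Section 14.4.2 and in the second SSID list of Section 14.4.3. This is free.

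(b) Choose one option, state it in Section 14.4.2 and carry it into the SAP:

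- **Gate and order.** Test the nine windows only if SPID 0–24 h is significant, then in a pre-listed fixed sequence. Each window keeps 0.05, but testing stops at the first failure.
- **Gate and Holm.** No order is needed, but a window with 80% power at 0.05 has 51% at the first step, and one with 90% has 68%.
- **Descriptive label.** No power is lost, but confirmatory claims on these windows are given up.

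A gate alone may be enough when correlations are high, but strong control of the error rate needs the order or the adjustment as well. None of the options touches the primary test. If the SAP already contains a rule, a citation in Section 14.4.2 is sufficient.

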#### 14.4.3 Other Secondary Analyses

The following other secondary endpoints for different time intervals will be compared between the 2 treatment groups using an ANCOVA model with the baseline pain/soreness score as the covariate.

- $SSID_{MOVE}$  over the following intervals: 0-6, 6-12, 0-12, 12-24, 0-24, 0-36, 24-48, and 0-48 hours post- $T_0$ . The mean  $SSID_{MOVE}$  for 0-6, 6-12, 0-12, 12-24, 0-24, 0-36, 24-28, and 0-48 hours post- $T_0$  will be compared between the 2 treatment groups (active versus vehicle) using an ANOCVA model with the baseline muscle stiffness score as the covariate.
- $TOTPAR_{MOVE}$  over 0-6 hours post- $T_0$ . An ANOVA model will be used for these efficacy endpoints.

$TOTPAR_{MOVE}$  A-B hr =  $\sum_{i=A}^{B-1} PR_i H$  where  $i$  refers to each pain relief scheduled assessment time point between A and B (not including B).

The TOPAR endpoints will be compared between the 2 treatment groups using an ANOVA model.

The subject's global assessment of efficacy will be assessed at approximately 48 hours post-T0 (or upon early termination if the subject withdraws prior to the 48-hour assessment). The distribution of 5 categories (poor, fair, good, very good, or excellent) will be compared between the 2 treatments (active versus vehicle) using the Chi-Squared test. In addition, the 5 categories will be dichotomized into 2 categories (good/very good/excellent versus poor/fair). The proportion of good, very good, and excellent ratings will be calculated for each treatment. This proportion will be compared between the 2 treatments (active versus vehicle) using the Fisher's Exact test.

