## 8 OVERVIEW OF STUDY DESIGN

This is a Phase 2/3, randomized, single-center, double-blind, vehicle-controlled, parallel-group study designed to determine the efficacy and safety of AP302 (CBI) (CBI) for the treatment of muscle pain/soreness associated with DOMS. Enough subjects will be screened to randomize 250 subjects.

Subjects will be screened up to 28 days prior to the Day 1. After completing the informed consent process, the following procedures will be completed: physical examination, medical history and concomitant medications collection, inclusion/exclusion criteria review, baseline laboratory testing, 12-lead electrocardiogram (ECG), pregnancy testing (females of child-bearing potential), drug and alcohol testing, and vital sign measurements.

Subjects who meet initial inclusion/exclusion criteria will be scheduled to return to the research center to undergo an exercise regimen (CBI)

Between (CBI) hours following the end of the exercise regimen, subjects will return to the clinic to be evaluated for eligibility into the active treatment phase of the study.

To qualify for randomization, subjects must report a (CBI)

CBI

CBI

Qualified subjects will be randomized to receive either AP0302 or vehicle control. CBI

CBI

CBI All doses and efficacy assessments will be completed while the subject is an inpatient at the study site. Subjects will be awakened for IP dosing and efficacy assessments as necessary.

Subjects will complete the following assessments at baseline:

- PI-NRS with movement
- Categorical Pain Rating score with movement (baseline only)
- Muscle Stiffness Numerical Rating Scale (NRS) with movement

The following assessments will be completed at CBI, CBI hours post-initial IP dose and immediately prior to the subsequent doses of IP:

- PI-NRS with movement
- Muscle Stiffness NRS with movement

The following assessment will be completed at CBI post-initial IP dose and immediately prior to a subsequent dose of IP if one occurs prior to CBI:

- Relief from starting pain with movement on the Categorical Relief Rating Scale.

At CBI post-initial dose (or prior to early termination, if applicable), the subject will complete a Subject Global Assessment to give their overall assessment of the IP.

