## 10.2 Efficacy Assessments/Endpoints

### 10.2.1 Primary Endpoint

The primary endpoint is the sum of the time-weighted pain intensity differences (PIDs) from baseline with movement (SPIDMOVE) over 0-24 hours post-T0 (SPIDMOVE 0-24 hours). Muscle pain/soreness with movement will be scored using the PI-NRS described in [Section 10.1.1](#) at the time points described in [Section 11](#). The PIDs from 0-24 hours after T0 will be calculated by subtracting each post-T0 pain score from the baseline (prior to T0) pain score. The weight given to each PID will be equal to the elapsed time since the previous evaluation.

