### CATEGORICAL RELIEF RATING SCALE

What word best describes your relief from starting pain?

- No relief (0)
- A little relief (1)
- Some relief (2)
- A lot of relief (3)
- Complete relief (4)

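### As printed, the TOTPAR 0-6 h formula gives a closing 6 h relief rating no weight, and the opening sentence of Section 14.4.3 names a model that neither of its bullets uses

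*Combined protocol and SAP*

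**What the plan says.** **TOTPAR.** Section 10.2.3 lists "Total relief with movement" over 0-6 h as an other secondary endpoint. Section 14.4.3 gives the formula: the sum of PR_i H from i = A to B-1, where i "refers to each pain relief scheduled assessment time point between A and B (not including B". The section defines neither PR_i nor H.

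**SPID, for comparison.** Section 14.4.1 uses the same limits, A to B-1, and also excludes B from the index. Each of its terms, however, is built from the "Mean of adjacent pain intensity differences" and weighted by the "elapsed time to the next evaluation". The general formula there contains PID at i+1 explicitly. Section 10.2.1 describes the weighting differently ("The weight given to each PID will be equal to the elapsed time since the previous evaluation"), but that rule keeps the closing rating too.

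**Baseline.** Section 8 introduces its list with "Subjects will complete the following assessments at baseline". The list holds the pain NRS, the categorical pain scale and the stiffness NRS. Relief is not on it.

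**Models.** The opening sentence of Section 14.4.3 assigns the other secondary endpoints an ANCOVA with baseline pain/soreness as covariate. The SSID bullet uses baseline muscle stiffness instead. The TOTPAR bullet, and the sentence after the formula, specify ANOVA.

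**The concern.** An index that stops before B is harmless when each term reaches forward to i+1, as in SPID. The TOTPAR formula keeps that index without the forward-reaching term. Taken literally, it leaves out the rating that closes the interval and starts from a T0 rating that the plan does not list. With H undefined as well, two programmers could follow the text and produce different scores for the plan's only relief endpoint.

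The model statements are a separate fault in the same section. The opening sentence matches neither bullet. Reading it as meant for SSID alone does not help, because its covariate still differs from the one in the SSID bullet.

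**Working it through.** The plan gives no numerical figure for TOTPAR, so there is none to reproduce. The check is the weight that each formula puts on each rating.

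**Inputs.** The formulas come from Sections 14.4.1 and 14.4.3. Appendix 2 codes relief from 0 to 4. The sample size is 250 (Section 14.3). Relief times are redacted, so the length L of the last interval before 6 h is assumed to be 1 h or 2 h, with a rating at 6 h.

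**1. Weight on the closing rating**
- As printed: sum of PR_i H for i = A to B-1. PR_B appears in no term, so its weight is 0, whether H is the time to the next rating or simply 1.
- Trapezoid rule of Section 14.4.1 applied to relief: sum of (t(i+1) - t(i)) × (PR_i + PR_(i+1)) / 2. PR_B appears only in the last term, with weight L/2.
- L = 1 h: 1/2 = 0.5 h. L = 2 h: 2/2 = 1.0 h.
- On the 0-4 scale the 6 h rating can therefore add up to 4 × 0.5 = 2 or 4 × 1.0 = 4 score units, against 0 as printed.
- A subject whose only relief is a rating of 2 at 6 h scores 2 × 0.5 = 1.0 or 2 × 1.0 = 2.0 by the trapezoid rule, and 0 as printed.

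**2. Effect on the last interval if H is the time to the next rating**
- Printed last term: L × PR_(B-1). Trapezoid last term: L × (PR_(B-1) + PR_B) / 2.
- Trapezoid minus printed: L × (PR_B - PR_(B-1)) / 2.
- Relief rising linearly to 2 at 6 h, L = 2 h: 2 × (2 - 1.333) / 2 = 0.667.
- The same rise, L = 1 h: 1 × (2 - 1.667) / 2 = 0.167.
- Relief flat over the last interval: 0. Relief falling: negative, so the printed rule credits more than the trapezoid.

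The weight moves to the preceding rating, so the direction of the difference depends on the relief profile.

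**3. Start of the sum**
- The first printed term is PR at T0 times H. With no T0 relief rating, the term is undefined unless a convention is set.
- With PR = 0 at T0, the first interval contributes nothing as printed. Under the trapezoid rule it contributes half the first post-dose rating times the interval length.

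**4. ANCOVA against ANOVA for TOTPAR**
- Residual degrees of freedom are 250 - 2 = 248 for ANOVA and 247 with one covariate.
- SE ratio, ANCOVA to ANOVA: sqrt((1 - r²) × 248/247), where r is the within-arm correlation of TOTPAR with baseline pain. The plan does not give r.
- r = 0.1 (assumed): sqrt(0.99 × 248/247) = 0.997, an SE about 0.3% lower.
- r = 0.3 (assumed): sqrt(0.91 × 248/247) = 0.956, an SE about 4.4% lower.

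**The case against.** The strongest reply is that the zero weight is not proved. Every relief time is redacted, and a 6 h rating is inferred only from the endpoint's label. PR_i is undefined and could have been meant as a mean of adjacent ratings. H may be the remnant of a symbol damaged in conversion. The SPID text also excludes B from its index and yet counts B, so that phrase alone shows nothing. Section 14 adds that "Detailed methodology for summary and statistical analyses of the data collected in this study will be documented in a Statistical Analysis Plan".

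Much of this stands, and it makes the practical effect conditional. It does not remove the fault. Section 14.4.1 spells out the adjacent mean and the weight; Section 14.4.3 has no counterpart to either, and its formula shows no i+1 term. No separate SAP text in the document reviewed settles the matter.

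On the models, it is fair to say that specific bullets normally govern a general opening sentence, so an analyst would probably use stiffness for SSID and ANOVA for TOTPAR. ANOVA is a valid analysis, and adjusting TOTPAR is a choice about precision. Eligibility based on at least some categorical pain level may also narrow the baseline range and push r down.

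A reader might infer more: that the treatment comparison is biased, that type I error is inflated, or that TOTPAR loses a large share of its value. The documents support none of these. The same scoring applies in both arms, and the last-interval difference can be positive, zero or negative. Differences totalled over the whole 0-6 h interval would mostly reflect the coarseness of the earlier steps, not the omitted 6 h rating.

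**Conclusion.** The point holds and is minor. Read literally, with PR_i as the rating at time i, Section 14.4.3 gives a 6 h relief rating zero weight. The plan's own trapezoid rule would give it 0.5 h or 1.0 h, for an assumed last interval of 1 h or 2 h. The sum also starts at a time with no listed relief rating. These results rest on a 6 h rating being scheduled and on the natural reading of PR_i; the missing definitions of PR_i and H do not depend on the schedule. The conflict between the opening sentence and its two bullets is plain on the page and independent of the formula. The primary SPID 0-24 h formula does not share the TOTPAR fault, and neither between-arm bias nor a type I error problem is shown.

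**What to change.** In Section 14.4.3, or in the SAP to be signed before database lock:

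- Define PR_i as the 0-4 relief rating at time t(i), and replace H with t(i+1) - t(i).
- Compute TOTPAR 0-6 h as the sum of (t(i+1) - t(i)) × (PR_i + PR_(i+1)) / 2, with the closing rating included. State PR = 0 at T0 as a convention.
- Keep baseline stiffness as the SSID covariate.
- Analyse TOTPAR by ANCOVA with the baseline pain score, and amend both ANOVA sentences to match. Present this as a precision gain of unknown size, not as the correction of an invalid test.
- Reword the opening sentence so that it states the model for each endpoint and agrees with the bullets.

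The cost is a few lines of text and the matching program specification. The baseline pain score is already collected, so no visit, assessment or sample size changes. Settling the wording before unblinding also removes a scoring choice that could otherwise be made with results in view.

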### 10.1.5 Subject Global Assessment

Subjects will rate their global assessment by answering the following question:

Overall, how would you rate the investigational product you received?

- Poor (0)
- Fair (1)
- Good (2)
- Very Good (3)
- Excellent (4)

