## 14.2 Randomization

Study drug will be assigned by predetermined randomization and distributed sequentially starting with the lowest available randomization number. Assignment to active and vehicle control will be in a 1:1 ratio.

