## 14.3 Sample Size Determination

A sufficient number of generally healthy subjects of either gender will be enrolled to obtain 250 randomized subjects. The sample size of 250 subjects (125 for each of the treatment group)

CBI

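### The ordered five-level Subject Global Assessment is tested with a Chi-Squared test that ignores the order; a rank test would be the better main test

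*Combined protocol and SAP*

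**What the plan says.** Section 10.1.5 asks the subject "Overall, how would you rate the investigational product you received" and offers five answers scored from Poor (0) to Excellent (4); Appendix 2 repeats the scale. Section 10.2.3 lists the subject's "global assessment of study medication assessed at approximately 48 hours" among the other secondary endpoints.

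Section 14.4.3 plans two comparisons. The five-level distribution is "compared between the 2 treatments (active versus vehicle) using the Chi-Squared test", with no trend or rank version named. The scale is then split once, between fair and good, and the share rated good or better is calculated for each arm: "This proportion will be compared between the 2 treatments (active versus vehicle) using the Fisher's Exact test".

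No rank, trend or ordinal-model analysis of this rating appears in the text. Section 14 says that detailed methods "will be documented in a Statistical Analysis Plan, which will be signed off prior to the database lock"; the document supplied contains no separate SAP section that adds to Section 14.4.3.

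**The concern.** The levels have a natural order, and the efficacy question is directional: do subjects rate active better than vehicle? The Pearson statistic sums a squared discrepancy over the columns of a 2x5 table, so shuffling the columns leaves it unchanged. It asks whether the two distributions differ in any way.

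Two things follow:

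- **Power.** A moderate, consistent shift toward better ratings is spread over 4 degrees of freedom when a rank test would concentrate it on one, so it may be missed.
- **Interpretation.** A significant result does not by itself show that ratings are better on active. It can arise when ratings only become more polarised.

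The Fisher comparison has a direction, but movement from poor to fair, or from good to excellent, does not register in it. How much it recovers depends on where the vehicle ratings fall relative to the cut, which is not known in advance.

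The stakes are limited to how efficiently and clearly one other secondary endpoint is read.

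**Working it through.** The plan states no power for this endpoint, so there is no figure of its own to reproduce.

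**Inputs from the documents**
- "All statistical testing will be performed with a 2-sided 0.05 level of significance" (Section 14.4).
- "The sample size of 250 subjects (125 for each of the treatment group" arm (Section 14.3; the justification that follows is redacted).
- "Assignment to active and vehicle control will be in a 1:1 ratio" (Section 14.2).
- Five ordered levels (Section 10.1.5), so the 2x5 table has (2-1)x(5-1) = 4 df.

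**Assumed, because the documents give nothing:** the vehicle distribution and the size and shape of the effect.

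**Check 1: no rating distribution needed.** Suppose the same signal (noncentrality λ) is tested on 1 df, as by a rank test of a consistent shift, and on 4 df. The 5% critical values are 3.841 and 9.488. Choose λ so that P(χ²₁(λ) > 3.841) equals the target power, then compute P(χ²₄(λ) > 9.488).

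| 1-df power | λ | 4-df power | Loss (points) |
|---|---|---|---|
| 0.50 | 3.84 | 0.31 | 19 |
| 0.60 | 4.90 | 0.39 | 21 |
| 0.70 | 6.17 | 0.48 | 22 |
| 0.80 | 7.85 | 0.60 | 20 |
| 0.90 | 10.51 | 0.74 | 16 |
| 0.99 | 18.37 | 0.95 | 4 |

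For 80% power the 4-df test needs λ = 11.94, which is 11.94/7.85 = 1.52 times the sample size.

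**Check 2: simulation.** 125 per arm, 20,000 trials per setting (Monte Carlo standard error at most √(0.25/20,000) = 0.0035). Vehicle percentages from Poor to Excellent were 20/25/30/15/10, 30/30/20/12/8 and 10/20/35/25/10. The active arm is a proportional-odds shift, in which the odds of being at or below each level are divided by OR. For the first distribution at OR 2.0, the odds of Poor go from 0.20/0.80 = 0.25 to 0.125, a probability of 0.125/1.125 = 0.111. Each cell gives the range over the three distributions.

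| OR | Chi-Squared | Wilcoxon (tie-corrected) | Fisher, good-or-better |
|---|---|---|---|
| 1.6 | 0.33-0.34 | 0.54-0.55 | 0.31-0.40 |
| 1.8 | 0.51 | 0.73-0.74 | 0.45-0.58 |
| 2.0 | 0.67-0.68 | 0.86-0.87 | 0.58-0.74 |
| 2.5 | 0.91-0.92 | 0.98 | 0.80-0.93 |
| 3.0 | 0.98 | 0.997-0.999 | 0.91-0.99 |

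A repeat with a different seed agreed to about 0.01. Wilcoxon minus Chi-Squared is 18-23 points at OR 1.6-2.0, about 7 at OR 2.5 and under 2 at OR 3.0. Against the better of the two planned tests, the gap at OR 1.6-2.0 is 13-23 points. In that range Fisher beats Chi-Squared for two of the three distributions. At OR 1, rejection rates are 0.048-0.053 (Chi-Squared), 0.049-0.052 (Wilcoxon) and 0.034-0.035 (Fisher).

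Five other assumed vehicle distributions (uniform, centred, low, very low, high) give the same picture. Wilcoxon versus Chi-Squared is 50-52% versus 30-32% at OR 1.57, 66-69% versus 44-47% at OR 1.73, and 81-82% versus 60-62% at OR 1.92. Fisher ranges over 21-37%, 29-53% and 39-68% at the same three effects.

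**Check 3: effects that are not a consistent shift**
- *No net shift* (vehicle 10/20/40/20/10, active 17/20/26/20/17): Chi-Squared is significant in 0.63 of trials, Wilcoxon in 0.055.
- *Poor and fair move only to good* (vehicle 20/25/30/15/10, active 13/17/45/15/10): Chi-Squared 0.58, Fisher 0.65, Wilcoxon 0.37.

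**The case against.** The strongest reply is that this is a preference between valid tests. Chi-Squared correctly answers whether the distributions differ, and the better choice depends on an effect shape that nobody knows. The poor/fair-to-good example shows the rank test losing. That stands, and it is why the Fisher comparison and the full table should stay.

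Second, the 20 points compare the rank test with only one of two planned tests, and the Fisher comparison already supplies a direction. At OR 1.6-2.0, at least one planned test is significant in 0.43-0.80 of trials, against 0.54-0.87 for Wilcoxon, a gap of only 6-13 points. This is not like for like: an either-test rule has a Type I error of about 7.3%, and the plan states no such rule. Taken singly, the better planned test is still 13-23 points behind. The direction that Fisher gives also holds at one cut-point only.

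Third, the no-net-shift example is constructed, and nothing in the documents suggests that polarisation is likely. That is fair. It shows what a significant Chi-Squared result can mean; it does not predict one.

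Fourth, Section 14 leaves detail to the SAP, and Chi-Squared test is not further specified, so an ordinal version could still be named there. True, but Section 14.4.3 already states a method, and its natural reading is Pearson's. The deferral makes the change easy to adopt; it does not make it unnecessary.

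**Conclusion.** The point holds as an improvement worth considering. It is not an error that threatens the trial. It is certain that the Chi-Squared test ignores the order and that no planned test uses the full scale. The loss of about 20 points is conditional: it assumes a consistent (proportional-odds) shift, 125 evaluable subjects per arm, and an effect for which a rank test has about 50-80% power. It shrinks for larger effects and reverses when the change is confined to part of the scale. Each planned test keeps its Type I error, and the SPID conclusion does not depend on this endpoint.

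**What to change.** In Section 14.4.3, or in the SAP before database lock:

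- Name the tie-corrected Wilcoxon rank-sum test (equivalently, Cochran-Mantel-Haenszel row mean scores with rank or ridit scores) as the main test of the five-level rating.
- Report the proportional odds ratio with its 95% CI. Section 14.4.3 currently gives no effect estimate for the five-level rating.
- Keep the good-or-better proportion with its planned Fisher's Exact test, labelled supportive.
- Tabulate all five levels by arm, so that a change confined to part of the scale stays visible.

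The cost is about one sentence of text, with no new data, visits or subjects. The price is lower power when the change is local or has no net direction. The supportive Fisher test covers the local change at the fair/good boundary examined above, though not one elsewhere on the scale.
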